### **8.3. Timelines for Submission of Safety Information:**

The timelines begin when the Investigator becomes aware of the event (i.e. during review of the medical records for the retrospective phase of the study or during the prospective phase of the study).

The Investigator will report to the Sponsor:

- As soon as possible, but no greater than **24 hours upon identifying the event, SADE, U(S)ADE and DevD that could have led to a SADE:**
  - if suitable action had not been taken
  - if intervention had not been made, or
  - if circumstances had been less fortunate
- During the prospective portion of the study, SAEs must be reported to the sponsor as soon as possible, but no greater than 24 hours of the investigator's awareness that the event meets SAE criteria.
- **Revisions, within 24 hours upon identifying the event.**

\* Retrospective SADE do not require reporting within 24 hours, but should be reported promptly, if a product complaint was not previously submitted to Smith & nephew Product Complaints

Investigators may also be asked to supply the Sponsor, upon Sponsor's request, with any additional information related to the safety reporting of a particular event.

The Principal Investigator (PI) will be responsible for reporting applicable adverse events to the IRB/EC of the study site per their institutional requirements, and to the regulatory authorities as required by the national regulations.

#### **8.4. Safety Reporting: Sponsor's Responsibilities**

The Sponsor will provide progress reports on safety events to the Investigator to report to the IRB/EC as required.

In the case of multicenter studies, the Sponsor will inform all Investigators in writing of all SADE that were reported by all sites throughout the clinical investigation and based on perceived risk.

The Sponsor will also, in case of SADE and device deficiencies that could have led to SADE, determine whether the risk analysis needs to be updated and assess whether corrective or preventive action is required.

### **9. STATISTICAL PROCEDURES**

Smith & Nephew Global Biostatistics Department will conduct statistical analysis. Unless otherwise stated, all significance tests and hypothesis testing will be two-sided, performed at the 5% significance level.

Where data summaries are specified, categorical and ordinal variables will be summarized using frequency distributions which will detail the number and percentage of subjects which fall into each category. Continuous variables will be summarized using the following summary statistics: mean, median, standard deviation, minimum and maximum values, and number of observations.

In formal analyses, resulting P-values will be quoted and 95% two-sided confidence intervals generated where appropriate. All analyses will be performed in SAS v9.4 (or later).

No formal interim analysis is planned.

#### **9.1. Sample Size Calculation**

This study will screen and consent patients until a total of 128 subjects, from up to 10 sites, treated with the study device have been enrolled in the study.

The study is intended to test for non-inferiority in the percentage of revision-free survival at 2 years recorded during the study compared to existing literature. The Australian Orthopaedic Association National Joint Replacement Registry 2015 Annual Report (13) records the revision-free survival for at 2-years as 95.7%.

Using a non-inferiority margin of 7%, a sample size of 115 subjects will provide at least 80% power at the 5% significance level using exact binomial methods. To allow for a 10% attrition and drop-out rate, a total of 128 subjects will be enrolled.

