#### **5. STUDY POPULATION**

##### **5.1. Subject Screening and Enrollment**

To eliminate the potential for selection bias, Investigators will consecutively screen subjects by date of surgery, starting with their first Navio-assisted UKR subject. For screening, only information in the medical records will be reviewed. Subjects meeting all eligibility criteria will be listed on a Screening and Enrollment log.

Once a subject has completed the informed consent process, if required by the IRB/EC, the subject will be considered enrolled and assigned a consecutive Subject Identification (ID) number that identifies a single study knee. The subject ID number will be listed on the Screening and Enrollment Log. In the event that a subject has bilateral Navio assisted UKR, only the first treated knee will be enrolled and assigned a Subject ID. The Screening and Enrollment Log is the source in which records all screening and enrollment details are recorded.

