## **5.2. Informed Consent**

Study sites will obtain IRB/EC approval for this study.

An IRB/EC waiver of informed consent for study participation should be requested for those subjects who meet eligibility criteria and have retrospectively completed a 2-year postoperative visit, are deceased, or are lost to follow-up, per IRB/EC policy. If allowed, a retrospective data set will be collected on these subjects. A copy of the waiver of informed consent will be placed in the subject file.

Subjects who meet eligibility criteria, are alive, and have not completed a 2-year postoperative visit, will be contacted and asked to provide Informed Consent prior to any retrospective or prospective data collection. These subjects may consent for participation only in the retrospective phase of the study or may consent for participation in both the retrospective and prospective phases of the study. The informed consent process will be documented in the subject's medical record and on the study Case Report Forms (CRFs). The informed consent form (ICF) will be placed in the subject file and a copy will be provided to the subject.

If a subject refuses participation, no further information will be collected. Reason for exclusion should be noted on the Screening and Enrollment Log.

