## **5.3. Subject Inclusion Criteria**

Subjects must meet the following inclusion criteria to be included in the study:

1. Male or female subjects  $\geq 18$  years old (at the time of surgery) who have undergone Navio System-assisted UKR prior to the date of IRB/EC approval of the study site. This includes UKR procedures with all Unicondylar Knee cemented implant designs.
2. Subject had a primary diagnosis of unicompartmental, non-inflammatory degenerative joint disease, including osteoarthritis, traumatic arthritis, or avascular necrosis, required correction of functional deformity, or required treatment of fractures that were unmanageable using other techniques.

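### Enrolment closes on a study-wide count of completed consents or waivers, not at a surgery date, so quickly entered waiver cases can displace earlier cases with consent pending and the series need not be consecutive.

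*Protocol*

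**What the plan says.** **Order of screening.** Protocol 5.1 states: "To eliminate the potential for selection bias, Investigators will consecutively screen subjects by date of surgery". Each investigator starts at the first Navio-assisted case. The requirement is about screening.

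**Moment of enrolment.** The same section continues: "Once a subject has completed the informed consent process, if required by the IRB/EC, the subject will be considered enrolled".

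**Two routes in.** Under Protocol 5.2, a consent waiver is to be requested for eligible subjects who "have retrospectively completed a 2-year postoperative visit, are deceased, or are lost to follow-up, per IRB/EC policy". Eligible subjects who "are alive, and have not completed a 2-year postoperative visit, will be contacted and asked to provide Informed Consent" must consent before any data are collected. Section 10.3 repeats both routes, adds patients who cannot be contacted to the waiver route, and says the waiver removes selection bias.

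**When it stops.** Protocol 9.1: "This study will screen and consent patients until a total of 128 subjects, from up to 10 sites". The only surgery-date limit in the eligibility criteria is that patients are those "who have undergone Navio System-assisted UKR prior to the date of IRB/EC approval of the study site" (5.3). No section sets a closing surgery date, a site quota, a hold for pending consents, or a rule that earlier cases be settled before later ones count.

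**The concern.** The study has one arm and compares its 2-year survivorship with a registry figure, so the result depends on an unselected case series. The protocol relies on consecutive screening to provide that, but the stopping rule does not carry the order through to enrolment. A waiver case can count as soon as it is listed, while a consent case counts only after contact and agreement. If the 128th place fills while earlier cases are pending, those cases drop out, even if every one of those patients would have agreed.

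This would matter little if speed of entry were unrelated to outcome, but it probably is related. Protocol 7.1 F ends participation at revision, with no later study data. A living patient revised before 2 years is thus less likely to have a completed 2-year visit on record and more likely to need consent. Losing such cases would raise apparent survivorship and the chance of passing the 88.7% bound. The link is an inference from 5.2 and 7.1 F; the documents do not state it.

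**Working it through.** **The plan's own figure.** Inputs from Protocol 9.1 and 9.4: reference 95.7%, margin 7 points, bound 88.7%, one-sided 95% exact interval. With n = 115, at most 7 revisions pass (lower bound 88.87%). The exact size at 11.3% is 4.5% and the power at 4.3% is 87.7%, so the stated 80% or more is met. Inflation: 115 / 0.9 = 127.8, rounded up to 128. The planned numbers are not in question.

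**Decision rule at 128.** At most 8 revisions pass (lower bound 89.0%). At a true revision risk of 11.3%, the chance of passing is 4.0%.

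**Illustration of displacement.** The documents give no eligible counts, consent times or route shares, so these are assumptions:
- The waiver is granted and all 128 outcomes are known.
- N = 160 or 200 eligible cases, half on each route.
- w is the share of revisions in the waiver half: 0, 25% or 50%.
- c is the number of consent cases among the 128. With no displacement c = 64. If all waiver cases go first, c = 128 − N/2, which is 48 for N = 160 and 28 for N = 200. Half-way priority is the midpoint, 56 or 46.

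Expected revisions entered: R = 0.113 × N × [(1 − w) × c/(N/2) + w × (128 − c)/(N/2)]. Entered risk: r = R/128. Chance of passing: P(X ≤ 8 | 128, r).

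Half-way priority:

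| N | w | R | r | Chance of passing |
|---|---|---|---|---|
| 160 | 0 | 18.08 × 0.70 = 12.66 | 9.9% | 10% |
| 200 | 0 | 22.6 × 0.46 = 10.40 | 8.1% | 28% |
| 160 | 25% | 18.08 × (0.525 + 0.225) = 13.56 | 10.6% | 7% |
| 200 | 25% | 22.6 × (0.345 + 0.205) = 12.43 | 9.7% | 12% |
| either | 50% | 14.46 | 11.3% | 4% |

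Complete waiver priority, as an extreme:
- w = 0: 23% (N = 160) and 82% (N = 200).
- w = 25%: 10% and 28%.
- w = 50%: 4%.

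**Under the SAP's rule.** SAP 7.10 uses a Kaplan-Meier estimate with a two-sided 95% interval. An exact analogue at 128 allows at most 7 revisions, so the formula becomes P(X ≤ 7 | 128, r). The baseline is 1.9%. Half-way priority with N = 160 and 200 gives 3.3% and 6.3% at w = 25%, and 5.5% and 17.5% at w = 0.

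**Effect on the estimate.** For a device truly at 4.3%, with N = 200, w = 0 and half-way priority, the entered risk is 0.043 × 200 × 0.46 / 128 = 3.1%.

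**The case against.** The strongest reply is that surgery order largely works against displacement. Screening starts at each site's first Navio case, and the earlier a surgery, the more likely a completed 2-year visit. Many waiver cases would therefore be entered early under any rule, and leaving out recent surgeries at closure is ordinary consecutive entry. This stands, and it confines the problem to older surgeries in living patients without a 2-year visit. It does not remove the problem, because a patient revised early may never complete that visit however long ago the surgery was.

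Other points also stand:
- The waiver depends on IRB/EC policy.
- A revised patient may still have a 2-year clinic visit in the chart. Revised patients who died, were lost or cannot be contacted are on the waiver route.
- The Screening and Enrollment Log lists eligible cases, so skipped ones could be traced afterwards. Neither the accountability report in Protocol 9.2 nor the table in SAP 7.6 asks for pending consents.

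A reader might infer that the series is certainly not consecutive, or that the rule does remove revised knees. The documents do not support that. They permit displacement, but it happens only if earlier consents are still pending at the 128th entry. Nor should the 82% figure be read as an estimate. It needs 200 eligible cases, every revision on the consent route, and all 100 waiver cases entered ahead of all but 28 consent cases.

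**Conclusion.** The point holds as a gap in the enrolment rule. Protocol 9.1 closes on a count of completed enrolments, only screening is ordered by surgery date, and nothing makes earlier cases resolve first. The plan as written can therefore yield a series that is not consecutive, despite the assurances on selection bias in 5.1 and 10.3.

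The likely direction favours the device, on the inference that living revised patients more often need consent. The size cannot be known from the documents. At the 11.3% limit, with half the eligible cases on each route and the protocol's rule, the chance of passing runs from 4% (no displacement, or revisions equally split), through 7-12% (a quarter of revisions in the waiver half, half-way priority, 160 to 200 eligible), to 10-28% (all revisions in the consent half, half-way priority). The figures are lower under the SAP's interval. The change is worth making because it is cheap and the comparison has no concurrent control.

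**What to change.** In Protocol 5.1 and 9.1, require each site to fill places in surgery-date order. Do not count a case toward 128 until every earlier eligible case at that site is recorded as consented, waived, refused, or unreachable after documented attempts. Stop at the surgery date at which the resolved runs reach about 128 in total. If refusals leave too few, extend each run forward in surgery order, with no choice based on outcome. Extending forward is safer than fixing a last surgery date in advance, which could leave fewer than the 115 needed for power.

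Report the four counts by surgery order in the accountability table of SAP 7.6.

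The cost is protocol wording, a short wait for pending consents, and a final number that may differ slightly from 128, which SAP 3 and 6.1 already treat as approximate. The planned 115 and 128 do not change. Refusals would still leave gaps, because under 5.2, "If a subject refuses participation, no further information will be collected"; their number should be reported.

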#### **9.2. Missing Data**

A complete accountability report, along with the explanation for lost-to-follow-up, death, revision, and withdrawn subjects is to be provided in the Clinical Study Report (CSR). The methods used to handle missing or incomplete data for the efficacy and safety measures will be detailed in the Statistical Analysis Plan (SAP).

### **9.3. Evaluability**

All subjects that receive a study device are considered study participants. The following study populations and analysis sets will be defined:

- Safety Population: This will include all subjects that received the study device.
- Full Analysis Set (FAS): This will include all subjects that received the study device.
- Per Protocol Population (PP): This will include all subjects that received the study device, meet the inclusion/exclusion criteria, attend the follow-up assessments, and have no significant protocol deviations. Subjects that are required to be withdrawn from the study under the protocol (e.g. due to revision) will be included regardless of attendance of follow-up visits unless they are deemed to have significant protocol deviations or failed to meet the inclusion/exclusion criteria.

Statistical analysis will be performed using each of the patient populations as follows: analysis of the primary, secondary efficacy objectives will be performed separately using both the FAS and the PP Population. All safety analyses will utilize the Safety Population.

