### **9.4. Analyses**

A formal SAP will be written and finalized prior to database lock. The SAP will detail the summaries and analyses to be performed.

- Primary endpoint:

The primary endpoint of the study is the Navio System assisted UKR revision rate at 2 years postoperatively. A one-sided 95% confidence interval for the revision [free] rate of the Navio System assisted UKR will be calculated using exact binomial methods. Non-inferiority, using a 7% non-inferiority margin will be declared if the lower bound of the confidence interval is  $>88.7\%$ . Time to occurrence of revision will also be analyzed using Kaplan-Meier survival analysis. Where appropriate, statistical modeling will be considered with prognostic and baseline factors adjusted for.

- Secondary endpoints:

Where appropriate, the secondary endpoints will be analyzed using either an ANOVA or Repeated Measures analysis, depending on whether a comparison between two time points or multiple time points is conducted. In each case, prognostic and baseline factors will be adjusted for. For endpoints where further analysis is not warranted, or not considered appropriate, tabulations detailing frequency distributions and/or summary statistics will be produced.

- Safety:

Numbers and types of AE, along with rates of AE types; with 95% confidence intervals for the rates (constructed using either exact binomial or asymptotic methods where appropriate) will be tabulated.

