7.2 Analysis Populations

Safety Population

This is defined as the population of subjects who receive the investigational study device.

Per Protocol Population

The per protocol population is the subset of subjects in the safety population who are compliant with the protocol by satisfying the following criteria: (a) meeting all inclusion/exclusion criteria (b) attend follow-up assessments and do not have significant protocol deviations.

Subjects who have a device revision would retain membership in the per protocol population unless any of the above two specifications is met. The final decision on which deviations would be classified as significant would be finalized prior to database lock.

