Cumulative proportions of subjects with implant survivorship at 2 years would be calculated and displayed accordingly. Subjects who complete the study without a revision would be censored at their last known date in the study. A subject who prematurely discontinues from study as a result of death or for any other reason would be censored at the date this event occurred. A subject who is lost to follow-up would be censored at the last known contact date. The Kaplan-Meier estimate for implant survivorship would be presented with the corresponding two-sided 95% Confidence Intervals (CIs). This study's hypothesis test would only be carried out at the end of the study at 2+ years (96 weeks). From this test, if the lower limit (LL) of the 95% two-sided CI for $S(t = 2 \text{ years}) > (\pi_0 - \delta) = 88.7\%$, then H_0 will be rejected in favor of H_a (i.e. demonstration of non-inferiority of the investigational device) otherwise H_0 would not be rejected. Kaplan-Meier estimates for implant survivorship would also be non-inferentially estimated at the intermediate time points of 6 months (24 weeks), 1 year (48 weeks), and at 18 months (72 weeks) as well as subsequently at 30 months (120 weeks).

The primary endpoint would be analyzed using the safety population as the primary analysis population while the per protocol population would be used for sensitivity analysis.

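### Per-protocol entry depends on the primary outcome, so the SAP's only named sensitivity analysis of survivorship is biased modestly downward and can contradict a Safety pass

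*Protocol*

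**What the plan says.** Protocol 9.3 makes attendance at follow-up a condition of PP membership, alongside eligibility and freedom from significant deviations. Subjects who have to be withdrawn under the protocol are exempt from attendance: "e.g. due to revision) will be included regardless of attendance of follow-up visits". The same sentence still removes them if they were ineligible or had significant deviations.

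SAP 7.2 repeats the attendance condition as "b) attend follow-up assessments and do not have significant protocol deviations". It says that revised subjects retain membership, but its exception is garbled: read literally, it would remove the revised subjects who satisfy the criteria. It does not repeat the protocol's attendance waiver. Neither document says which assessments must be attended.

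On the primary endpoint the two documents differ in method. Protocol 9.4 plans an exact binomial analysis: "A one-sided 95% confidence interval for the revision [free] rate of the Navio System assisted UKR will be calculated using exact binomial methods". Protocol 9.3 asks for it in both the Full Analysis Set (FAS) and PP, with no rule for disagreement. SAP 7.10 uses Kaplan-Meier, censors lost subjects at last contact, and compares the lower two-sided 95% limit with 88.7%. It decides on the Safety population, and "the per protocol population would be used for sensitivity analysis".

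**The concern.** A sensitivity analysis is informative when its analysis set is chosen without regard to the outcome. Here a knee that fails is kept without attending, while a knee that has not failed is dropped if the visit was missed. The numerator of failures is preserved and the event-free denominator shrinks, so estimated survivorship falls even when non-attendance has nothing to do with revision.

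Kaplan-Meier does not need this filter, because a subject with no 2-year visit contributes event-free time up to last contact and is then censored. What is at stake is interpretation. PP is the only sensitivity analysis the SAP names for the primary endpoint. A PP lower limit below 88.7% after a Safety pass would be read as fragility, when it may only reflect how the set was built.

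**Working it through.** **Inputs from the documents.** Control survivorship 95.7%, margin 7 points, threshold 95.7 − 7 = 88.7%; 115 evaluable, 10% attrition, 128 enrolled (Protocol 9.1, SAP 6.1).

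**Assumed inputs.** Non-attendance of 20% and 30%; loss independent of revision; exponential revision times; non-attenders last seen uniformly over 0–1.9 years and the others at 2.0–2.6 years. The SAP names no confidence-interval transformation, so log-log and plain limits are both shown.

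**Step 1: the plan's own figure.** The protocol states that "a sample size of 115 subjects will provide at least 80% power at the 5% significance level using exact binomial methods". Exact binomial at n = 115, one-sided 5%: up to 7 revisions are allowed, attained alpha is 0.0446 and power at 95.7% is 87.7%, so the statement holds. 115 / 0.9 = 127.8, giving 128.

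**Step 2: direction and upper size, closed form.** Let p be the revision risk, d the share of unrevised knees dropped, and suppose every revision is known. Then S_PP = (1 − p)(1 − d) / [(1 − p)(1 − d) + p]. With p = 0.043 and d = 0.10: 0.8613 / 0.9043 = 95.2%, against 95.7%. For d = 20% and 30% the result is 94.7% and 94.0%.

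**Step 3: Kaplan-Meier.** The shift is smaller here, because a revision after last contact is not known and so does not enter PP either. Simulation with 128 subjects, 6,000 trials per setting, Greenwood variance; PP = known revisions plus 2-year attenders:

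| Non-attendance | Mean S(2 y), Safety | Mean S(2 y), PP | Safety passes, PP fails: log-log | Same: plain |
|---|---|---|---|---|
| 10% | 95.7% | 95.5% | 6% | 5% |
| 20% | 95.7% | 95.2% | 16% | 9% |
| 30% | 95.7% | 94.9% | 25% | 17% |

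Repeat runs moved these by about one point at most. PP never passed when Safety failed.

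**Step 4: bias or set size?** An outcome-neutral comparator drops all non-attenders, revised or not; its mean stays at 95.7%. In one set of 5,000 trials per setting, Safety-pass/PP-fail under log-log limits was 5.8 / 16.6 / 25.5% for the written rule and 4.1 / 9.6 / 14.2% for the neutral set. More than half of that discordance is therefore ordinary loss of precision. Under plain limits the figures were 5.4 / 9.0 / 16.5% against 3.5 / 4.7 / 6.4%.

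Net pass rates under log-log limits give the bias more weight. Safety was 74 / 70 / 66%, the neutral set 72 / 64 / 54%, and PP as written 68 / 54 / 40%. The step from neutral to written is 4 / 10 / 14 points of a total 6 / 16 / 26. The two views differ because a neutral set sometimes passes where Safety fails, and the written PP does not.

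**Step 5: one case.** Take 13 of 128 lost without revision and 8 revisions, with both spread over the two years and plain limits. The Safety lower limit is 89.0% and passes. In PP, S = 107/115 = 93.04%, SE = √(0.9304 × 0.0696 / 115) = 2.37 points, and the lower limit is 93.04 − 1.96 × 2.37 = 88.4%, which fails. The protocol's exact one-sided 95% limit splits in the same way: 120/128 gives 89.0% (taking lost knees as revision-free) and 107/115 gives 87.8%. Exactly 8 revisions among 128 has probability 8.6% at the assumed rate.

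**The case against.** The strongest reply is that the waiver is there for a reason. Under Protocol 7.1 a revision ends participation and data collection, so an attendance rule without a waiver could push revised knees out of PP. Survivorship would then be biased upward, the worse error in a non-inferiority study. That stands, and the waiver should not simply be deleted.

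The attendance condition also has a purpose under Protocol 9.4: an exact binomial analysis cannot censor and needs a known 2-year status. It is redundant only for the SAP's Kaplan-Meier analysis.

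A reader might infer that PP can reverse the non-inferiority conclusion. The documents do not support that. SAP 7.1 and 7.10 decide on the Safety population, so PP can only disagree, and its bias runs against the claim and cannot create a false one. Nor is every revised knee kept: ineligible or deviating ones still leave. The waiver is not confined to revision either, since Protocol 7.1 also requires withdrawal if the study is stopped.

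Two limits remain. At the planned 10% the effect is small, and a visit may be done by telephone (Protocol 6.3), so true non-attendance is unknown. And if lost knees were revised elsewhere, the Safety estimate is itself too high and a lower PP figure would not be mere artefact. The present rule does not test for that, because it drops such knees and does not examine them.

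**Conclusion.** The concern holds in a limited form. PP membership depends on the primary outcome. If loss is unrelated to revision, Kaplan-Meier survivorship in PP is biased downward by about 0.2 points at the planned 10% attrition, and by about 0.5 and 0.8 points at an assumed 20% and 30%. Depending on the transformation, PP contradicts a Safety pass in about 5–6%, 9–16% and 16–26% of trials. Under log-log limits, roughly half or more of that is due to the smaller set and not to the bias. The SAP decision is not at risk and the error is conservative. What is lost is the value of the only named sensitivity analysis: a PP failure could not be told apart from an artefact of the set. These sizes rest on a true survivorship of 95.7% and on the assumed timing of loss. The change is worth making before database lock.

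**What to change.** For the Kaplan-Meier analysis of the primary endpoint:

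- Define PP by eligibility and absence of significant deviations only, applied identically to revised and unrevised knees.
- State that a missed visit alone does not exclude a subject. Protocol 12 counts out-of-window visits as deviations, so silence would leave this open.
- Censor unrevised knees without the 2-year visit at last contact, as SAP 7.10 already provides.
- Align Protocol 9.3 with SAP 7.2 and repair the SAP's exception for revised knees.

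The cost is a short text change in both documents, with no new data. There is a downside: PP may come close to the Safety set, and with no other exclusions it equals it. So add a worst-case or tipping-point analysis for knees of unknown 2-year status. It also covers the protocol's exact binomial analysis, where censoring is not available. Tipping-point is the more useful of the two. At n = 128 and one-sided 5% the exact test allows 8 revisions, so counting 13 lost knees (128 − 115) as revised would fail even with no observed revision.
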